## SYNOPSIS OF RESEARCH CONTINUED

### **Introduction**

Cytomegalovirus (CMV) infection is the most common congenital infection worldwide and the leading cause of non-genetic sensorineural hearing loss (SNHL) in childhood. Prevalence of congenital CMV infection ranges from 0.6 to 5% dependent on the population studied. Up to 17% of all infected newborns are at risk of permanent neurologic sequelae, including SNHL; motor, cognitive and visual impairment; microcephaly; seizures and cerebral palsy. Morbidity data on congenital CMV infections has mostly been from high income countries (HIC). It is necessary to establish whether congenital CMV infection in South African children presents the same public health impact as in high resource countries and determine the effect of HIV on CMV infection.

### **Aim**

The aim of this project is to determine the epidemiology of congenital CMV infection and incidence of neurological sequelae until 12 months age in a high HIV prevalent setting in Soweto, Johannesburg.

### **Methods**

This study will be nested within a larger cohort study of 35000 mother infant dyads to investigate a sero-correlate of protection against invasive GBS disease (HREC 140203) currently underway at Chris Hani Baragwanath Academic Hospital (CHBAH) in Soweto. A cross sectional study design screening 2200 mother-newborn pairs enrolled in V98\_28OBTP that consent to this study will be undertaken identifying cases of congenital CMV by saliva PCR. A longitudinal cohort study following up the cases of congenital CMV matched to a CMV negative cohort of newborns will measure the incidence of and risk factors for neurological sequelae until infants are 12 months of age. To measure the association between congenital CMV infection and neonatal death and stillbirths, a longitudinal study on causes of death in under 5 children by Minimally Invasive Tissue Sampling (MITS), which is currently underway (HREC 150215), will include tissue processing for CMV. Maternal CMV seroprevalence will be determined by serological methods as well as the association between vaginal CMV shedding and congenital CMV infection.

These studies will identify CMV seroprevalence in pregnant women which is thought to be high (>70%) and will determine the prevalence of congenital CMV infection in Soweto through universal newborn screening which has only previously been done in symptomatic newborns at CHBAH. This study will also provide the first estimates on the incidence of SNHL and other neurological impairment in CMV infected newborns, adding to the current discussions on increasing resource allocation to universal newborn hearing screening. The measure of the effect of HIV exposure on the prevalence of congenital CMV and the burden of subsequent neurological disability will add to the growing global knowledge on congenital CMV in various settings impacting the prevention, diagnosis and management of infected infants.

## 1 Introduction

Cytomegalovirus (CMV) infection is the most common congenital infection worldwide and the leading cause of non-genetic sensorineural hearing loss (SNHL)\* in childhood. Global prevalence of congenital CMV infection is estimated at 0.64%, varying across countries (0.2 – 6%) with higher prevalence's in lower and lower- middle income countries (LMIC). Seventeen percent of all infected infants are at risk of permanent neurological disability. The impact of congenital CMV infection in neonates is not well recognised as it is mainly asymptomatic at birth with the inability to attribute neurological impairment in children retrospectively to *in-utero* CMV infection.

### 1.1 Biology and Immunology of CMV

Human CMV is a DNA virus of the Herpesviridae family and viral transmission occurs through body fluids (blood, saliva, breast milk, vaginal fluid, semen and urine) spreading to multiple organs (kidney, liver, lung, brain). CMV demonstrates strain diversity and mixed infection with multiple strains in an individual is common, whilst immunity to CMV is strain specific.

Following primary infection, the virus establishes lifelong persistence and is usually asymptomatic in the immunocompetent. Secondary infection occurs with reactivation of a latent virus or infection with a new strain in a previously CMV seropositive person. Strain specific antibodies (IgM and IgG) and a broad T cell response is activated, limiting viral replication and preventing disease, although unable to completely eliminate the virus.

### 1.2 Epidemiology of Congenital CMV Infection

**Maternal infection:** Low socioeconomic status, black race, crowded living conditions and younger age are associated with higher CMV seroprevalence. Consequently, maternal seroprevalence may be over 80% in LMIC. A maternal CMV seroprevalence of 86.6% was found in a South African study but is expected to vary with socioeconomic disparity. Primary infection in HIC commonly occurs in adulthood and in women of reproductive age, during

pregnancy In lower resource settings CMV infection occurs at young age when exposed to infected maternal saliva, breast milk and because of over-crowded conditions.

**Congenital infection:** Viral transmission to the foetus can occur through the maternal-foetal placental interface increasing with gestational age. Foetal effects of infection are more severe if infected in the first 16 weeks of gestation when organs are developing and may lead to abortion and stillbirths Transmission rates are higher during primary maternal infection (30 -35%) compared to women with secondary infection (1.4%). Counterintuitively, there is greater prevalence of congenital CMV in high CMV seroprevalent populations compared to low seroprevalent populations who are at higher risk of primary CMV infection. This is explained by there being more pregnant women at risk of CMV reactivation and reinfection in high seroprevalent populations coupled with other risk factors. A recent systematic review of studies from LMIC, showed population based congenital CMV prevalence ranging from 0.6 – 6.1% (e.g. Panama 0.6%, Gambia 5.4%, China, 6.1%) compared to 0.2-2.0% in HIC (Chile 0.2%, USA 1.2%, Finland 2.0%).

**Diagnosis of congenital CMV infection:** CMV isolation by culture or positive polymerase chain reaction (PCR) test in urine, saliva, blood or tissue taken at biopsy within the first 2 weeks of life is diagnostic of congenital CMV. Acquired CMV during delivery can be detected after 2 weeks incubation and CMV isolation beyond 2 weeks age cannot reliably be concluded as *in utero* infection. CMV PCR in urine and/or saliva is favoured as the standard of diagnosing congenital infection.

**Clinical significance and long term outcome of congenital CMV:** Most newborns with congenital CMV are asymptomatic at birth (85-90%). Of the 10-15% of symptomatic newborns clinical manifestations range from mild, non-specific findings to multi-organ system involvement. The most frequent signs are petechiae, jaundice and hepatosplenomegaly. Central nervous system (CNS) signs include microcephaly, hearing impairment, chorioretinitis and/or

optic atrophy and seizures. Of the symptomatic neonates, about 50% are small for gestational age, 33% are born prematurely and 5% die in the neonatal period.

Permanent neurological sequelae occurs in 40-58% of symptomatic and 14% of asymptomatic infants at birth. Children with symptomatic birth infection may have multiple neurological sequelae including SNHL (30-60%), cerebral palsy and mental retardation (50-80%) visual impairment (20-35%) and neurodevelopmental behaviour disorders (30-60%). The most common sequela in infants asymptomatic at birth are SNHL (10%) with other complications occurring at a lower frequency: motor deficits (5%) and chorioretinitis (2%).

**Effect of HIV:** An estimated 3% of congenital CMV infection occurs in HIV exposed infants compared to 1% in HIV unexposed infants. HIV infected infants have an even higher prevalence of congenital CMV (10.3%) as found in a French perinatal cohort. In this study, HIV and CMV co-infected newborns had a 3-fold greater risk of symptomatic congenital CMV infection at birth (23%) than HIV exposed but uninfected infants (6.7%). CMV co-infection may also contribute to HIV disease progression with increased risk of mortality and faster progression of CNS disease in survivors. However, the incidence of vertical CMV transmission in HIV infected women decreased following introduction of antiretroviral therapy (ART) during pregnancy.

Data on congenital CMV infection among HIV exposed infants in sub-Saharan Africa are limited. A Kenyan study of infants born to mothers on perinatal Zidovudine, identified congenital CMV rates of 29% (4/14) in HIV-infected infants and 2.7% (1/37) in HIV exposed but uninfected infants. Zambian newborns admitted to a referral neonatal unit had a congenital CMV prevalence of 3.8% (15/395) whilst prevalence in HIV exposed newborns was 11.4% (9/79). Although HIV prevalence in South African pregnant women is one of the highest in the world (29.9%), a single study has evaluated the relationship between congenital CMV and HIV exposure. In Cape Town, Manicklal et al (2013) found a congenital CMV prevalence of 2.9% (22) in 748 HIV exposed babies. Maternal CD4+ count <200 cells/µL was independently

associated with congenital CMV. Clinical outcomes in these infants and prevalence of congenital CMV among HIV unexposed newborns were not investigated.

**Perinatal and Postnatal CMV infection:** Perinatal CMV infection is defined as CMV infection after 22 completed weeks (154 days) of gestation and seven completed days after birth. Postnatal CMV acquisition is CMV infection acquired any time after birth through consumption of breast milk from CMV seropositive, lactating mothers is common. Most term infants with perinatal CMV infection are asymptomatic, as maternally transferred CMV IgG antibody provides adequate protection against disease. However, studies have identified a significant risk for low-birth-weight (LBW), premature infants for the development of CMV disease such as pneumonia, hepatitis or sepsis-like illness. Data on severity and incidence of disease and long term impact in these infants is currently lacking requiring further study.

**Current therapeutic options:** Treatment for maternal and newborn CMV infection is limited. Anti-CMV hyperimmunoglobulin is efficacious in preventing transmission from primary maternal infections but its value in secondary infection is uncertain. Some European countries offer universal maternal CMV screening or foetal anomaly ultrasonography to identify ventriculomegaly, intracerebral calcification and microcephaly. Foetal infection is confirmed by amniocentesis, not commonly available in LMIC, and women may be offered termination of pregnancy. Targeted CMV screening in symptomatic newborns and/or fail universal hearing screening occurs in the USA. Screening programmes have not been widely implemented due to lack of awareness, high costs and lack of rapid diagnostic tests. Ganciclovir (GCV) or Valganciclovir is administered to symptomatic CMV infected neonates, associated with improved audiologic outcomes. However GCV's effectiveness in asymptomatic cases has not been fully assessed. Both symptomatic and asymptomatic infants should be monitored regularly for neurological disability.

**Economic Impact:** The effect of congenital CMV disease on quality of life and cost to the health system led the Institute of Medicine (IOM) in the USA (1999) to declare development of a CMV vaccine as a highest priority. The IOM estimated that approximately \$1.9 billion per year is spent toward medical and educational costs for congenitally CMV infected children in the USA compared to costs of developing a CMV vaccine of \$360 million. The health economic implications of congenital CMV in low income countries is under-recognised or unknown.

**Impairment of immune response** The efficacy of infant vaccines in Sub-Saharan Africa has consistently been lower than in high income countries for a number of vaccines (e.g. measles vaccine, rotavirus vaccine). It has been postulated that CMV infection, due to its large recruitment of T-cells may have a role to play in modulating immune responses to infant vaccinations but only a few groups thus far have investigated this in children.

**Problem statement** Morbidity data on congenital CMV infections has largely been from HIC as a result of maternal primary infection, whereas data from low-income, high secondary infection and high HIV prevalent settings are lacking. In the South African public health sector, only symptomatic newborns have CMV testing whilst newborn hearing screening is conducted in high risk babies born premature, symptomatic or admitted to ICU. Asymptomatic, CMV infected infants at birth are an at risk group of developing disabilities which only become apparent when children are older and interventions less effective. Studies have demonstrated up to 15% of stillbirths have lab confirmed CMV infection. Any association between neonatal deaths and congenital CMV infection is yet to be described.

### 1.3 Justification for the study

There is no robust data on the immunology, virology, mortality, disease and disability burden from congenital CMV infection in South Africa. The effect of HIV on congenital CMV and subsequent neurological sequelae is also largely unknown in black Africans. Early detection of SNHL and neurodevelopmental disorders could enable timely intervention to improve quality of

life. If sequelae are significantly higher in HIV exposed infants, this study may contribute to discussions towards a targeted screening programme for CMV in HIV exposed infants. With the development of a CMV vaccine in progress, it is necessary to establish baseline disease epidemiology determining whether congenital CMV infection in South African children presents the same public health impact as in high resource countries and whether screening programmes or a vaccine is necessary or cost effective in our setting. Most available data suggest that antibody positivity, is not associated with protection from vertical transmission to a foetus or infant or with protection from re-infection. However, some studies suggest that antibody avidity and/or neutralisation activity may be associated with protection from vertical transmission. We wish to explore this further and also assess if either measure is associated with maternal HIV infection.

## **2 Aim and Objectives**

The theme of this project is to determine the epidemiology of congenital CMV infection and incidence of sequelae until 13 months age in a high HIV prevalent setting in Soweto, Johannesburg.

### **2.1 Primary Objectives:**

2. 1. Determine the CMV seroprevalence, antibody avidity and (if possible) anti-CMV neutralising antibody activity in blood plasma of both HIV infected and uninfected pregnant women at the time of delivery and explore associations between these measures and risk of congenital and postnatally acquired CMV infection in the first year of life. To compare the prevalence of congenital CMV infection and incidence of symptomatic infection in HIV-exposed and HIV-unexposed neonates

3. To determine the incidence and risk factors for neurological sequelae in congenitally CMV infected neonates from birth up to 12 months of age compared to a control group of neonates without congenital CMV
4. To determine by minimally invasive tissue sampling (MITS) the association between congenital CMV infection and: 1) Neonatal deaths less than 3 weeks of age and 2) Stillbirths

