**Table 2: Maternal and newborn data of interest**

Maternal data	Newborn data
Demographic: age, race, and contact details	Demographic: date of birth, gender, race
Clinical data: antenatal care details, past obstetric history, parity, gestation at delivery, delivery details, co-morbidities, HIV status and CD4 count, ART use	Clinical: gestational age at birth, birthweight, head circumference, APGAR scores, HIV exposure, symptoms at birth, discharge or admission details

Newborn saliva samples will be collected by placing an Orocot swab in the mouth for at least 1 minute. All symptomatic neonates for congenital CMV infection ([Appendix 11](#)) will also be screened for other congenital infections which include syphilis, toxoplasmosis, rubella and herpes as is the standard of care at CHBAH.

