**Figure 1: Data collection process for Objectives 1, 2 and 5**

All children with any clinical finding are referred to the neonatology department at CHBAH for clinical management as per standard of care. If a newborn PCR indicates CMV infection, the mother will be contacted telephonically to return to the site within two weeks of birth. At this visit the implications of the positive CMV result will be explained and additional consent for the continued follow up of the child (refer to [Appendix 7](#) for ICF and [Appendix 8](#) for schedule of study visits). Should consent be confirmed, a second saliva swab and a urine sample will be collected for PCR to confirm CMV infection. Babies that test CMV negative on both the second saliva swab and urine will not be enrolled as a case as the saliva positivity may be a result of CMV infected breast milk contamination. However, they will be referred for hearing screening as standard of care. Cases testing positive on both saliva and urine or urine alone will continue as cases for objective 3.

Mothers of CMV cases will have a vaginal swab and breast milk collected for quantitative PCR by a research nurse or the investigator. A subset of mothers that tested seropositive for CMV but gave birth to CMV uninfected neonates will also be recalled as controls for the case mothers in a

1:1 ratio, matched by HIV infection, for vaginal fluid and breast milk collection within 2 weeks of delivery.

**Sample size:** Objective 1: Assuming the estimated CMV prevalence is 86% in pregnant women 200 mothers will be needed to estimate the true value with a desired precision of 5% and confidence interval of 95%.

Objective 2: Prevalence of congenital CMV in HIV exposed neonates is 2.9% and in unexposed neonates is 1.0%. Thus, a total sample of 1662 neonates with 831 HIV exposed and 831 unexposed (1:1 ratio) for 80% power, are required to detect a 2.9 fold difference in CMV prevalence between the 2 groups. This will be increased to 2160 neonates, to accommodate objective 3, to determine clinical sequelae in CMV infected infants ([section 3.3.1, Sample size](#)). After adjusting for 10% being non-evaluable, 1077 HIV exposed (providing 31 CMV infected) and 1077 HIV unexposed infants (providing ~11 CMV cases) are required. Ranges of sample size estimates for varying CMV prevalences by HIV exposure are given in [Appendix 9](#).

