**Table 3: Data analysis plan**

Objective	Data Analysis
1. Determine the seroprevalence of Cytomegalovirus infection (CMV) in HIV infected and uninfected pregnant women attending CHBAH	Table of maternal demographic and clinical characteristics as proportions
	Maternal CMV seroprevalence expressed as a percentage stratified by HIV status (95% confidence interval)
	Chi square test to compare reactivations/recurrent infections determined by IgG avidity and IgM presence compared to latent infection stratified by HIV status
2. Compare the prevalence of and risk factors for congenital CMV infection in HIV exposed and unexposed newborns	Prevalence of congenital CMV infection in HIV exposed and unexposed infants expressed as a percentage with 95% confidence interval
	Multiple regression analysis to adjust for potential confounders: gender, gestational age at birth, birth weight, birth order, symptoms at birth
	In HIV exposed infants, chi square tests for association between: 

- Congenital CMV infection and maternal ART use

- Congenital CMV infection and severity of maternal immunosuppression (CD4+ count levels)

To explore the association between maternal CMV shedding in vaginal fluid and breast milk and the risk of congenital CMV infection assessed by quantitative CMV PCR.	Chi square test for association between vaginal CMV shedding and congenital CMV infection 

- Stratify by varying ranges of viral shedding (high, moderate, low – quantification to be determined)

- Stratify by HIV infection though will have low power for this

**Potential challenges:** Objective 1, 2 and 5: Mothers may be reluctant to be enrolled in a study for an infection which is unknown to them. To mitigate this, a patient information leaflet will be provided to improve understanding and includes the potential benefit to the infant should he/she

be diagnosed to have congenital CMV ([Appendix 7](#)). Training of researchers in effective communication will be conducted.

Objective 5: CMV viral shedding is cyclical, highest during primary infection; reactivation or reinfection which when occurs during pregnancy may be transmitted to the foetus. This study may be limited by the collection of samples after delivery at which point, viral shedding may have ceased since pregnancy.

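### Primary Objective 2 promises a comparison of symptomatic congenital CMV by HIV exposure, but the body text plans no analysis of it; the numbers support description only, with uninfected newborns as the background

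*Combined protocol and SAP*

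**What the plan says.** Section 2.1 names two comparisons by HIV exposure under Objective 2: "To compare the prevalence of congenital CMV infection and incidence of symptomatic infection in HIV-exposed and HIV-unexposed neonates".

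Table 3 in section 3.3 restates the objective without the second one: "Compare the prevalence of and risk factors for congenital CMV infection in HIV exposed and unexposed newborns". The rows beneath it are:

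- an estimate for each HIV group: "Prevalence of congenital CMV infection in HIV exposed and unexposed infants expressed as a percentage with 95% confidence interval";
- a multiple regression adjusting for "potential confounders: gender, gestational age at birth, birth weight, birth order, symptoms at birth";
- chi-square tests of congenital CMV against maternal ART use and CD4 count, within HIV-exposed infants.

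The sample size text in section 3.3 rests on infection prevalence alone: "a total sample of 1662 neonates with 831 HIV exposed and 831 unexposed (1:1 ratio) for 80% power". It expects 31 infected infants among 1077 HIV-exposed newborns and about 11 among 1077 unexposed.

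Three other places matter. Section 1.2 puts 10-15% of infected newborns as symptomatic, says that their signs extend from mild and non-specific ones upward, and adds "The most frequent signs are petechiae, jaundice and hepatosplenomegaly". Table 2 lists, for newborns without restriction to CMV-positive ones, "HIV exposure, symptoms at birth, discharge or admission details". The text under Table 2 has symptomatic neonates tested for syphilis, toxoplasmosis, rubella and herpes, and refers to Appendix 11 for what counts as symptomatic.

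**The concern.** Half of a primary objective has no estimator, denominator or sizing in the body text. Someone following the plan would either leave the question unanswered or choose an analysis after seeing the data. The denominator alone (all screened newborns or infected newborns) changes what the result means.

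The simplest way to fill the gap is to count signs among infected infants in each HIV group. Signs such as jaundice have causes other than CMV, so some infected infants will show them by coincidence. If such signs are commoner in HIV-exposed newborns for other reasons, that count would show an HIV effect on CMV disease where none exists.

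The one planned use of symptoms raises a separate problem. In a model of congenital CMV, symptoms at birth can result from the outcome. Adjusting for them may distort the HIV association, and it does not yield the comparison that the objective names.

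Section 1.3 links higher sequelae in HIV-exposed infants to possible targeted screening, so findings by HIV exposure may carry weight in practice.

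**Working it through.** **1. The plan's own sizing.** Inputs from section 3.3: 2.9% v 1.0%, 1:1, 80% power. Two-sided 5% alpha is assumed, as none is stated for this calculation. With pooled variance and no continuity correction, and mean prevalence 0.0195:

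n per group = [1.96 x sqrt(2 x 0.0195 x 0.9805) + 0.842 x sqrt(0.029 x 0.971 + 0.010 x 0.990)]^2 / 0.019^2 = 831, total 1662.

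This reproduces the stated figure. At 1077 per group the power for prevalence is 89%.

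**2. Expected symptomatic infants.** Infected: 1077 x 0.029 = 31.2 exposed; 1077 x 0.010 = 10.8 unexposed. At 10-15% symptomatic:

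- exposed: 31 x 0.10 to 0.15 = 3.1 to 4.7;
- unexposed: 11 x 0.10 to 0.15 = 1.1 to 1.7.

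The 31 and 11 use all 1077. With 10% non-evaluable (969 per group) they become 28 and 10.

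**3. Precision.** Exact (Clopper-Pearson) 95% intervals among infected infants: 4/31 = 13% (4 to 30%); 1/11 = 9% (0.2 to 41%).

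**4. Power per newborn screened.** Fisher's exact test, 1077 per group, same symptomatic proportion in both HIV groups, so that the only difference is the assumed 2.9-fold prevalence ratio:

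- 10% symptomatic: risks 0.0029 v 0.0010, power 4%;
- 15% symptomatic: risks 0.00435 v 0.0015, power 10%.

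**5. Background signs.** Let s be the risk of CMV-caused signs among infected infants and b the risk of the same signs from other causes. If the two are independent, the observed risk is 1 - (1 - s)(1 - b). The documents give no value for b, so the rates below are assumptions. With s identical in both HIV groups, an infected-only comparison shows:

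| b exposed v unexposed | s = 5% | s = 10% | s = 15% |
|---|---|---|---|
| 6% v 5% | 0.107/0.0975 = 1.10 | 0.154/0.145 = 1.06 | 0.201/0.1925 = 1.04 |
| 10% v 5% | 0.145/0.0975 = 1.49 | 0.190/0.145 = 1.31 | 0.235/0.1925 = 1.22 |
| 20% v 10% | 0.240/0.145 = 1.66 | 0.280/0.190 = 1.47 | 0.320/0.235 = 1.36 |

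Every ratio would be 1.00 if only CMV-caused signs were counted. Subtracting the CMV-negative rate within each HIV group leaves s(1 - b). For 20% v 10% and s = 10%, that is 8% v 9%, so the spurious excess goes.

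**6. What the subtraction can resolve.** Screened negatives: 1077 - 31 = 1046 exposed; 1077 - 11 = 1066 unexposed. Approximate 95% half-width = 1.96 x sqrt[p(1 - p)/n infected + b(1 - b)/n negative]:

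- exposed: 12.5 points at p = 14.5%, b = 10%; 15.1 points at p = 23.5%, b = 15%;
- unexposed: 17.6 points at p = 9.75%, b = 5%; 25.1 points at p = 23.5%, b = 15%.

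Nearly all of this imprecision comes from the few infected infants.

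**The case against.** Much can be said on the other side.

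- **No infected-only count is planned.** A reader might infer that the protocol sets out to count signs in infected infants alone. It does not; it sets out no analysis at all. The attribution problem concerns the likeliest way to fill the gap.
- **Symptom data from CMV-negative newborns are not wholly unused.** The Objective 2 regression, if fitted to all screened newborns, draws on them and relates symptoms to CMV status. That stands, but as covariate adjustment it gives neither symptomatic infection by HIV exposure nor a background rate within each HIV group.
- **The power case can be overstated.** Section 1.2 quotes 23% v 6.7% symptomatic, and with 31 v 11 infected infants Fisher power at those risks is only 7%. That contrast, however, is HIV-infected v HIV-exposed uninfected infants, not exposed v unexposed. The objective can also be read per newborn: with 1077 per group those same risks give 53%. So the 7% should not be presented as the power of the objective. The 4-10% above avoids the borrowed contrast.
- **No single bias ratio is established.** A figure such as 1.5 is one point in an assumed range. A modest background difference gives almost none.
- **Some attribution work is planned.** Testing symptomatic neonates for four other congenital infections helps, but does not cover causes such as prematurity.
- **Two appendices were not available.** Appendix 3 summarises objectives and analysis, and Appendix 11 defines symptomatic infection. Either could narrow the point; a strict definition would shrink the background share.

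**Conclusion.** The point holds in a limited form. In the body text and Table 3, a stated primary comparison has no analysis, and the only use of symptoms in the Objective 2 rows treats a possible consequence of infection as a confounder. The expected 3-5 v 1-2 symptomatic infants support description, not a test; this rests on the plan's prevalences and its 10-15% symptomatic. Non-specific signs could create an apparent HIV effect, by a ratio of about 1.04 to 1.66 over assumed backgrounds of 6% v 5% to 20% v 10% and CMV effects of 5-15%. Its true size cannot be determined from the documents.

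A reader might go on to infer that Objective 2 as a whole is undermined. The documents do not support that: the sizing for infection prevalence reproduces exactly and is unaffected. The change should be made before analysis.

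**What to change.** In the Objective 2 rows of Table 3, section 3.3:

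- **(a)** Add symptomatic congenital CMV per 1000 screened newborns by HIV exposure, with exact 95% confidence intervals and the denominator stated.
- **(b)** Add, within each HIV group, the prevalence of the same signs in CMV-positive and in all CMV-negative screened newborns, as a risk difference with a confidence interval and with gestational age taken into account. Use signs recorded at birth only, because PCR-positive infants are recalled and would otherwise have more chance of a sign being noted.
- Label both rows descriptive, and change the verb for symptomatic infection in section 2.1 from compare to describe.
- Remove symptoms at birth from the confounder list of the Objective 2 model.
- Check both rows against Appendices 3 and 11, so that the definition of symptomatic infection and the analysis summary agree.

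The cost is two table rows on data that Table 2 already lists, plus a check that signs are recorded alike for all screened newborns. The downside is that a primary comparison becomes descriptive, and the excess-risk estimate stays imprecise: half-widths of about 12.5 to 15 points in exposed and 18 to 25 points in unexposed infants.
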